Clinical Investigation Plan

CP353

A randomized, open-labelled, crossover study confirming performance of a single-use intermittent micro-hole zone catheter in a population of adult male intermittent catheter users.

July – December 2022

Date: August 2, 2022

NCT05485922

CHANGE LOG

VERSION NUMBER	ISSUED BY (INITIALS)	COMMENTS (MAJOR CHANGES SINCE LAST REVISION)
1.0		First approved version

This confidential document is the property of Coloplast A/S.
No unpublished information contained herein may be
disclosed without written approval of Coloplast A/S.

Exploratory endpoints:

- Pressure measurement at first flow-stop derived from a catheterisation profile, [mbar]
- Post-catheterization volume post catheterisation measured with a bladder scanner assessed by the average of 3 consecutive measurements [mL]

Population/subjects:

The clinical investigation will be conducted in 42 subjects enrolled in 1-3 clinical investigation sites in Denmark and USA.

To be included in the investigation, the subjects must comply with the selection criteria described below:

Inclusion criteria	Exclusion criteria
1. Is Male	1. Is participating in any other clinical study during this investigation
2. Is at least 18 years of age and has full legal capacity	2. Has previous participated in this study
3. Has given written informed consent	3. Has symptoms of urinary tract infection as judged by the investigator
4. Has signed letter of authority (only DK)	4. Is an individual with history, suspected or showing signs of producing urine with excessive amount of mucus or large/clustered sediments or debris
5. Has used clean intermittent catheterisation CH12 or CH14 for at least one month	5. Has any known allergies towards ingredients in the investigational device
6. Use intermittent catheterisation as the primary bladder emptying method	
7. Is able (assessed by investigator) and willing to follow study procedures	

> TABLE OF CONTENTS

1 List of personnel involved in the Investigation	8
2 Rational/justification for conducting the clinical investigation	8
3 Objective(s) and hypotheses of the clinical investigation	8
3.1 Objective (s)	8
3.2 Hypotheses.....	8
4 Investigational device and comparator(s)	9
4.1 Description of investigational device	9
4.1.1 Manufacturing	9
4.2 Identification and traceability of the device	9
4.3 Intended use of the device in the clinical investigation	10
4.4 Intended population for the device	10
4.5 Handling of the investigational device	10

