4.7 Description of the comparator product(s)

The comparator will be Hollister VaPro, a single-use hydrophilic sleeved soft/flexible catheters in the sizes CH12 (Item 72124) or CH14 (Item 72144). Hollister Vapro is CE-marked in EU and 510k-cleared in the US.

As the comparator devices are already on the market and will be used within the intended use in this investigation, it is not considered an investigational device according to ISO 14155:2020 and is thus not described into further details here.

Coloplast A/S will provide comparator devices to sites.

To ensure that the site has enough supplies, more investigational devices than needed will be provided by Sponsor to the site. All investigational devices will be accounted for both prior to and after use.

5 Design of the clinical investigation

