5.1 General

The investigation is a multi-centre, randomised, controlled crossover study including 42 male IC users.

The total study duration for the individual subject will be between 3 days to 2 weeks, consisting of three site visits. Visits 0 is an information visit and can be combined with V1 if subjects prefer. For visit 1 and 2, one catheterization will be performed in the hospital setting by a health care professional assessing flow stop episodes, bladder emptying and haematuria. Visit 2 can be performed the day after visit 1, or maximum 14 days after visit 1.

The study design and procedures are described below in Figure 5-1.

[figure not shown]

Figure 5-1 Study design

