5.6 Demography and potential compromising factors

The following baseline data will be collected and registered at visit 1(V1) by the investigator or designee:

- Date of informed consent
- Date of visit
- Age
- When did you start using a catheter? (months or years)
- Average number of catheters used per day during the last month
- Current device brand/type (can choose more than one)
 - Braun Actreen
 - Bard
 - Bullens
 - CliniMed
 - Coloplast
 - Convatec
 - Cure
 - Hollister
 - Manfred Sauer
 - TeleFlex
 - Wellspect
 - Oasis
 - LentisMed

- Second sequence: The comparator, then the investigational device.

Randomisation will be centralized using Medidata RAVE, see section 11.

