6.1.1 Inclusion criteria

For a subject to be eligible, all inclusion criteria must be answered "yes":

Inclusion criteria	Justification for inclusion criteria
1. Is Male	Intended patient population of investigational and comparator devices.
2. Is at least 18 years of age and has full legal capacity	Intended patient population of investigational and comparator devices. To meet Helsinki Declaration.
3. Has given written informed consent	To ensure that the subject has been given written and oral information regarding the investigation and know enough about the investigation to decide on participation. To ensure voluntariness and that Helsinki Declaration is met.
4. Has signed letter of authority (only DK)	Letter of Authority is a demand from Danish Medicines Authorities.
5. Has used clean intermittent catheterisation CH12 or CH14 for at least one month	To ensure that the subject is used to catheterization.
6. Use intermittent catheterisation as the primary bladder emptying method	To ensure that the subject is used to catheterization.
7. Is able (assessed by investigator) and willing to follow study procedures	To ensure sufficient data for successful completion of the study.

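### Every randomised man is allocated to both catheters, but the allergy exclusion, as worded in the synopsis, names only the investigational device

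*Combined protocol and SAP*

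**What the plan says.** Section 5.1 sets the design: "The investigation is a multi-centre, randomised, controlled crossover study including 42 male IC users". It adds: "For visit 1 and 2, one catheterization will be performed in the hospital setting by a health care professional". The surviving line on the randomisation sequences reads "Second sequence: The comparator, then the investigational device".

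The synopsis lists seven inclusion and five exclusion criteria. Exclusion 5 is the only one about allergy: "Has any known allergies towards ingredients in the investigational device".

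Section 4.7 describes the comparator as an already marketed product that "will be used within the intended use in this investigation", and on that ground states that "it is not considered an investigational device according to ISO 14155:2020 and is thus not described into further details here".

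Two other places bear on what the term covers. In section 6.1.1 the justification for the first two inclusion criteria names the products separately: "Intended patient population of investigational and comparator devices". In section 15, on device accountability, the plan counts comparators among the investigational devices.

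**The concern.** In a parallel-group trial each subject would meet one product. Here each subject is due to meet both, so an allergy rule that covers one product covers half of what he is exposed to. A site that applies the list as written, and reads the term as section 4.7 defines it, has no criterion on which to refuse a man who reports a known allergy to an ingredient of the comparator. Under section 10.2, subjects who do not meet the criteria are screening failures and are not randomised. This man fails none of them.

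Two things are at stake. The first is avoidable exposure to a product despite a known allergy to it. In the comparator-first sequence that product is his first study device. The second is data. If the allergy comes to light only after randomisation, the comparator period may not take place, his within-subject device contrast is lost, and a replacement may be needed under section 6.3.

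**Working it through.** The plan gives no figure to reproduce, and the point does not depend on alpha, power or a variance. The check sets the passages side by side.

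1. **Who is due to receive the comparator?** Section 5.1 gives a crossover with one catheterisation at each of visits 1 and 2. Each sequence therefore contains each device once, and all 42 planned subjects are allocated to the comparator (42/42).

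2. **What does exclusion 5 cover?** It names one device, in the singular. Section 4.7 expressly places the comparator outside the class of investigational devices. Read together, exclusion 5 does not reach the comparator.

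3. **Does another criterion cover it?** The other four exclusions concern participation in another study, earlier participation in this one, symptoms of urinary tract infection, and urine with excess mucus or sediment. The seven inclusions concern sex, age and legal capacity, consent, the Danish letter of authority, at least a month of CH12 or CH14 catheterisation, catheterisation as the main emptying method, and ability and willingness to follow procedures. None mentions allergy to the comparator.

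4. **Is prior tolerance of the comparator implied?** No. The month of catheterisation may be with any brand, and section 5.6 lists many. The comparator's manufacturer is only one of them.

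5. **Could the term be read more widely?** Section 15 does so. Against that, section 4.7 is the express statement of the comparator's status, exclusion 5 is singular, and the eligibility table names both products where it means both. The narrower reading is better supported, but the plan's usage is inconsistent.

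6. **How many men?** The documents give no allergy prevalence. Purely as an assumption, for 0, 1 or 2 affected men among 42 the share of pairs concerned is 0/42 = 0%, 1/42 = 2.4% or 2/42 = 4.8%. These figures restate the assumption and estimate nothing.

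One limit on the text: in the copy available for this review the table in section 6.1.2 is visible only as far as criterion 3. The finding therefore rests on the synopsis wording. Whether section 6.1.2 words criterion 5 the same way, or justifies it with reference to both devices, could not be checked.

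**The case against.** The strongest reply is that the gap is one of wording and that ordinary safeguards would catch such a man. Relevant medical history is taken at visit 1 and is listed ahead of randomisation in the visit schedule. His current catheter brand is recorded. Section 17 requires that he be told of potential risks and given at least 24 hours to decide. Inclusion 7 asks the investigator to judge him able, and him to be willing, to go through the study procedures, which include both catheterisations. The comparator is to be used within its intended use. Section 6.3 allows withdrawal in the subject's interest and requires it if his safety is compromised. This stands in part: exposure despite a known allergy would need several safeguards to fail. But none of them is an allergy criterion, and the withdrawal rule acts only after entry. The sponsor did not leave allergy to the investigational device to judgement, and no visible passage explains why the comparator should differ.

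The second reply is that lost data are already provided for. This largely stands. Withdrawn subjects can be replaced (section 6.3), the full analysis set keeps anyone exposed to at least one device with one endpoint recorded (section 10.2), and the mixed models with a random subject term (section 10.4) can use data from a single period.

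A reader might infer more than the text supports:

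- **That exclusion 5 cannot cover the comparator.** Section 15 shows that the plan sometimes uses the term for both products.
- **That an affected man has a contraindication to the comparator.** Its ingredients and contraindications are not described in the documents.
- **That one-sided screening biases the adverse device effect comparison towards the investigational device.** The screening is asymmetric on the narrower reading, but no expected event rate is given and no visible hypothesis test compares these events. Section 11.2 rests pass or fail on the two primary endpoints alone. A distortion is possible but not shown.

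**Conclusion.** The point holds as a gap in the eligibility wording. It rests on the synopsis text of exclusion 5 and on reading it with section 4.7 rather than section 15. On that reading, no visible criterion screens for known allergy to a product that all 42 men are allocated to receive. On the wider reading the criterion is ambiguous, and an ambiguous safety criterion still needs correcting.

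The gain from correcting it is subject safety and, secondarily, avoiding an occasional lost comparator period. The number of men affected is unknown and may be zero. No effect on power, alpha or the primary conclusion is shown. The documents also do not establish that an affected man would in fact be catheterised with the comparator, only that no written criterion prevents it. The change is worth making because it is cheap and the exposure is preventable.

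**What to change.** Reword exclusion 5 so that it covers known allergy to ingredients of either the investigational or the comparator device. Make the change in the synopsis, in section 6.1.2 (after checking its present wording) and in the eCRF eligibility form, and have the criterion checked before randomisation. At the same time reconcile the terminology of sections 4.7 and 15, so that the plan says in one place whether its term for the investigational device includes the comparator.

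Sites will need the comparator's ingredient information to apply the criterion, because section 4.7 does not give it. Otherwise the cost is a few words in the plan and the form, and at most a very few men screened out. Sample size, visits and analysis are unchanged.

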4.1 Description of investigational device

The investigational device is a ready-to-use, sterile, hydrophilic-coated male catheter for intermittent catheterisation. The device is for single use only and is intended to be used for drainage of the bladder through the urethra by people with missing or reduced bladder control.

The investigational device has a flexible tip (Flex tip) that facilitates passage through the sphincter in the urethra and is compositionally identical to the already CE-marked SpeediCath® Flex. The only difference is the design and manufacturing method of the drainage holes.

The device is intended to be used by male catheter users in this clinical study.

The investigational device includes a coating system to reduce surface friction. A sleeve around the investigational device keeps the coating and catheter sterile through insertion.

The drainage end of the investigational device has an outlet to which a urine bag with a suitable connector can be connected. At the end of the sleeve there is a guide tip to help protect the user not to touch the catheter shaft and make it easier to insert the catheter.

The primary packaging provides the sterile barrier of the investigational device and contains tear opening as a proof of seal for identification of used devices. All legally required information is presented on the investigational device primary packaging.

The investigational devices are sterile by radiation.

The investigational devices are neither CE-marked in EU nor 510k-cleared in the US.

4.2 Identification and traceability of the device

All investigational devices are labelled as per regulations and include "Exclusively for Clinical Investigational" on the label. The devices are also identified with study number, device name/code, and item/lot number and is accounted for through a master sponsor accountability log.

Figure 4-2 illustrates the labels for the investigational devices.

4.7 Description of the comparator product(s)

The comparator will be Hollister VaPro, a single-use hydrophilic sleeved soft/flexible catheters in the sizes CH12 (Item 72124) or CH14 (Item 72144). Hollister Vapro is CE-marked in EU and 510k-cleared in the US.

As the comparator devices are already on the market and will be used within the intended use in this investigation, it is not considered an investigational device according to ISO 14155:2020 and is thus not described into further details here.

Coloplast A/S will provide comparator devices to sites.

To ensure that the site has enough supplies, more investigational devices than needed will be provided by Sponsor to the site. All investigational devices will be accounted for both prior to and after use.

5 Design of the clinical investigation

5.1 General

The investigation is a multi-centre, randomised, controlled crossover study including 42 male IC users.

The total study duration for the individual subject will be between 3 days to 2 weeks, consisting of three site visits. Visits 0 is an information visit and can be combined with V1 if subjects prefer. For visit 1 and 2, one catheterization will be performed in the hospital setting by a health care professional assessing flow stop episodes, bladder emptying and haematuria. Visit 2 can be performed the day after visit 1, or maximum 14 days after visit 1.

The study design and procedures are described below in Figure 5-1.

[figure not shown]

Figure 5-1 Study design

5.2 Primary endpoints

- Number of flow-stop episodes derived from a catheterisation profile, [number].
- Residual volume at 1st flow-stop i.e., post catheterisation volume minus volume at 1st flow-stop, both derived from a catheterisation profile, [g].

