5.3 Exploratory endpoints

- Pressure measurement at first flow-stop derived from a catheterisation profile, [mbar]

[figure not shown]

Figure 5-2 Overview of measurements during and after catheterisation.

Microtrauma: Concentration of microscopic haematuria and incidences of positive haematuria indicates possible catheter-associated microtrauma. With the micro-hole zone catheter, fewer mucosal suctions and putatively less or no co-sequential blood in the urine is expected. This is based on previous literature showing mucosal suction and associated trauma with indwelling catheters (Glahn, 1988; Glahn et al., 1988; Grocela & Jura, 2010; Milles, 1965), which has also been demonstrated with conventional 2-eyelet intermittent catheters in the preclinical setting (Coloplast A/S, 2021b, 2021c) (data not yet published).

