Descriptive statistics for continuous variables are presented with N, Mean, SD (standard deviation), Median, Min and Max, where N denotes the number of subjects contributing with non-missing data. For discrete variables, descriptive statistics are presented with N and percentage, where percentage is based on the total number of subjects/observations with non-missing data.

All statistical analysis will be performed with SAS (version 6.4/Enterprise Guide version 7.1).

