10.2 Definition of analysis populations

Screening Failures (SF), Intention to Treat (ITT), Full Analysis Set (FAS), Safety and Per Protocol (PP) analysis set will be defined at a formal data review meeting prior to database lock. As a minimum, the data manager, the clinical manager, and the statistician will be involved in the classification of subjects.

Subjects not adhering to inclusion and/or exclusion criteria are considered screening failures (SF) and are not randomised.

The Safety population will constitute all subjects enrolled i.e., subjects who have given informed consent.

The ITT population will constitute all randomised subjects.

The full analysis set is a modified ITT population i.e., a sub-population of the ITT population, and will constitute all randomised subjects, who have been exposed to at least one device, with at least one endpoint recorded (data non-missing).

The PP is a sub-population of the full analysis set where all subjects have received treatment as per protocol.

Individual endpoints/data points may be excluded from the analysis, even though the corresponding subject belongs to any of the pre-defined populations. Exclusion of subjects or data points must be documented.

All statistical analysis and test of hypothesis will be based on the full analysis set, and in addition, Primary and Secondary endpoints will also be analysed in the PP population, if the PP population differs from the full analysis set. whereas adverse events and device deficiencies will be assessed in the safety population.

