10.4 Analysis of the primary endpoints

- Residual volume at first flow-stop, will be analysed in a general linear mixed model with subject included as a random component. Evidence of superior effect will be concluded, if the 95% confidence interval of the difference between comparator and investigational device, do not include zero.
- Number of flow-stop episodes will be analysed, in a generalized linear mixed model, with subject included as a random component. Evidence of superior effect will be concluded, if the lower 95% confidence limit of the risk ratio between comparator and investigational device, is more than 1.

The models will include following fixed effects.

- Visit (visit 1 and 2 of catheterisation)
- Device (comparator and investigational device)

The power for concluding superiority of the investigational device is at least 90% or higher.

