11.2 Pass/fail criteria

To demonstrate superiority of the investigational device, the null hypothesis of the primary endpoints must be rejected, at a 5% significance (alpha 0.05).

The pass criteria for the study are based on the results from analysing the two primary endpoints in a hierarchical fashion: rejecting the null-hypothesis on the first endpoint (Residual urine at first flow-stop) before continuing to the second (Number of flow-stop episodes).

12 Data management

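### Is the first-tested endpoint left without a value when a catheterisation has no flow-stop?

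*Combined protocol and SAP*

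**What the plan says.** Section 5.2 has two primary endpoints: a count of flow-stop episodes, and a residual defined as "Residual volume at 1st flow-stop i.e., post catheterisation volume minus volume at 1st flow-stop, both derived from a catheterisation profile, [g". Section 10.4 gives the model for the second: "Residual volume at first flow-stop, will be analysed in a general linear mixed model with subject included as a random component", with visit and device as fixed effects. Although 5.2 lists the count first, section 11.2 sets the order of testing by "rejecting the null-hypothesis on the first endpoint (Residual urine at first flow-stop) before continuing to the second (Number of flow-stop episodes", and section 10.3 makes this a fixed sequence at the 5% level. The residual is therefore the gate to the count.

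The schedule in 7.1 lists the urine volume at first flow-stop at visits 1 and 2, with no condition attached. Section 5.3 lists a related exploratory measure in the same unconditional way: "Pressure measurement at first flow-stop derived from a catheterisation profile, [mbar". Section 12.1 has two specialists read the sensor profiles independently and reconcile their readings before upload.

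**The concern.** The definition needs a first flow-stop. If urine drains without interruption, the term to be subtracted has no stated value, and the visible text does not say whether the natural end of flow counts as a stop.

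The general data rules would let a blank through unnoticed. The full analysis set in 10.2 takes randomised subjects "who have been exposed to at least one device, with at least one endpoint recorded (data non-missing", so a subject with a count but no residual stays in. The descriptive-statistics paragraph reports N "where N denotes the number of subjects contributing with non-missing data". The mixed model would simply use the residuals that exist.

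Blanks might also fall unevenly. The microtrauma paragraph printed after 5.3 says: "With the micro-hole zone catheter, fewer mucosal suctions and putatively less or no co-sequential blood in the urine is expected". If suction is what causes flow-stops, which is an inference, uninterrupted catheterisations would be more frequent on the investigational device. Its best results would then be the ones dropped. The comparison would be conditional on an outcome of treatment, and randomisation would not protect it. Because this endpoint is the gate, a failure here would also stop the test of the count.

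**Working it through.** **1. The plan's own power figure.** Section 10.4 states power of at least 90%; section 5.1 gives 42 subjects in a crossover. At two-sided 5%, the standardised paired difference this implies is (1.960 + 1.282)/√42 = 3.242/6.481 = 0.50 (0.51 with a t distribution on 40 df). The effect, SD and flow-stop rates behind the 90% are not in the visible text. The figure can therefore be neither reproduced nor used to infer how an uninterrupted catheterisation was treated.

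**2. What the definition gives when flow is uninterrupted.** Write residual = V(end) − V(first stop). If flow first stops when the bladder is empty, V(first stop) = V(end) and the residual is about 0 g. No imputation is needed. This reading also fits the schedule in 7.1 and the pressure endpoint in 5.3, both of which expect a value each time.

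**3. Where a rule could sit.** The table of contents lists 5.4 (assessments), 5.5 (rationale and measurement of endpoints) and 5.7 (equipment and methods). In the public copy 5.4 and 5.7 do not appear, and 5.5 survives only as the microtrauma paragraph. Of "Figure 5-2 Overview of measurements during and after catheterisation" only the caption remains. The synopsis names a second exploratory endpoint that 5.3 no longer shows, so text has been lost at this spot. The hypotheses in section 3, the sample-size text and part of section 10 are also not shown.

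**4. What blanks would do, under assumptions.** Let pC and pI be the flow-stop rates on comparator and investigational device, m the comparator's mean residual given a flow-stop, and r the ratio of the two conditional means.

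- Uninterrupted counted as 0 g: difference = m(pC − r·pI).
- Uninterrupted left blank: difference ≈ m(1 − r).
- Ratio, blank to 0 g = (1 − r)/(pC − r·pI), which equals 1 when r = (1 − pC)/(1 − pI).

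With r = 0.5, the 80/40 case gives 0.5/(0.80 − 0.20) = 0.83. The power columns come from simulating the 10.4 model with 42 subjects. The inputs are assumed, not taken from the plan: m = 60 g, SD 50 g, gamma residuals, within-subject correlation 0.4.

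| pC / pI | Ratio, blank to 0 g | Power, 0 g | Power, blank | Mean complete pairs if blank |
|---|---|---|---|---|
| 95% / 90% | 1.00 | 0.99 | 0.99 | 36 |
| 95% / 80% | 0.91 | 1.00 | 0.98 | 33 |
| 80% / 40% | 0.83 | 1.00 | 0.77 | 15 |
| 60% / 40% | 1.25 | 0.94 | 0.69 | 13 |
| 60% / 20% | 1.00 | 1.00 | 0.26 | 7 |

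These figures move with the assumptions. For SD from 30 to 70 g, the 80/40 blank power runs from 0.99 to 0.37. With Wald instead of t limits, the 60/20 blank power is 0.52.

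**5. A second set of assumptions.** This used lognormal residuals with CV 1, log-scale correlation 0.3 and a paired t-test on complete pairs. With both conditional means at 50 g and rates of 90% and 30%, 0 g gives 50 × (0.9 − 0.3) = 30 g and 92% power; blanks give about 0 g and 2%. With means of 50 and 25 g and 90% on both devices, the differences are 0.9 × (50 − 25) = 22.5 g and 25 g, with power 88% and 89%.

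**6. Does the 0 g reading upset the planned model?** In the simulation of step 4, with equal flow-stop rates from 20% to 95%, upper-side type I error was 0.019 to 0.024 against a nominal 0.025. It does not.

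**The case for a change.** The strongest case for acting is that this endpoint is the gate, the trial is open-label, and the profiles are read at the sponsor. A convention fixed before reading starts removes a choice that could otherwise be made with results in view. It would cost one sentence, with no new data and no new model. If flow-stops are uncommon on the investigational device, blanks could decide the outcome.

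Part of this stands. The visible text is silent, and whatever convention is used should be the same for the residual, the count and the pressure measure. Asking the sponsor where a flow-stop is defined is a reasonable neutral question.

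The rest does not establish a fault. The silence is in a copy from which the relevant sections are missing. The wording in 10.2 and the descriptive-statistics paragraph is standard and applies to every endpoint; it is not evidence that residuals would be blank. The harm requires an analyst to discard a catheterisation that drained completely, when the plan's own subtraction gives it a value and the schedule asks for one.

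**Conclusion.** No change is needed. This is at most a detail missing from the visible text, and the plan's own definition fills it sensibly: an uninterrupted catheterisation has a residual of about 0 g and stays in the model. No visible rule produces a wrong result.

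The conclusion rests on two points: that the definition may well stand in text not shown, and that the natural reading of 5.2 with 7.1 gives a value at every visit. No effect size can be assigned to this trial. Under the assumptions above, blanks would be harmless when flow-stops are common on both devices and serious when they are uncommon on the investigational device; the shift in the estimate could be nil or go in either direction. The visible documents do not say which case applies, and they give no sign that blanks are intended.
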